**e Weight/Height:** Height is required at baseline only. Weight is required at Screening and prior to starting each infusion. The total dose will be calculated based on the weight on the day of the infusion or the most recent weight assuming it was assessed in a reasonable time frame according to Investigator assessment. Study sites should make every effort to measure body weight as close to the infusion day as possible considering the variability of local process from site to site. If the infusion is prepared with the most recent weight assessed in a reasonable time frame, this will not prevent to assess the weight on D1 of each cycle.

- f* For participants with known HIV, hepatitis B and hepatitis C infection under antiviral treatment to confirm controlled infection, and for all participants in Germany and Italy (see details and specific instructions in [Section 10.2](#) and [Section 10.8](#)).
- g* If a tumor biopsy was obtained from a target lesion during eligibility assessment, it is preferred to obtain a new baseline scan.
- h* **CT/MRI:** The initial tumor imaging will be performed within 28 days prior to the C1D1. Scans performed as part of routine clinical management are acceptable for use as the screening scan if they are of diagnostic quality and performed within 28 days prior to the date of enrollment. On study imaging will be performed every 9 weeks (63 ±7 days) after the date of first IMP or more frequently if clinically indicated in the first 45 weeks. Imaging studies should follow calendar days and should not be adjusted for delays in cycle starts or extension. The same imaging technique should be used in a participant throughout the trial. After Week 45 tumor imaging should be performed every 12 weeks (84 ±7 days). CT scan of the **head, neck, chest and abdomen (pelvis is optional)** and any other locations with suspicion or evidence of disease involvement is required for the baseline assessment and during treatment period until PD. After the first documentation of response or the first documentation of progression (if the participant is clinically stable) per RECIST 1.1, confirmatory imaging should be performed no fewer than 28 days later. Alternately, the scan performed at the next scheduled time point (eg, every 63 ±7 days) may be used as confirmation. Tumor assessment is not needed for participants who start another anti-cancer therapy.

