#### Type of participant and disease characteristics

- I 02. Histologically or cytologically confirmed diagnosis of R/M HNSCC that is considered not amenable to further therapy with curative intent. The eligible primary tumor locations are oropharynx, oral cavity, hypopharynx, and larynx (nasopharynx is excluded).

- I 03. Measurable disease

At least 1 measurable lesion (not biopsied at baseline) per RECIST 1.1 criteria. Target lesion(s) may be located in a previously irradiated field if there is documented radiographic disease progression of such lesion(s).

- I 04. Known HPV p16 status for oropharyngeal cancer.

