### Medical conditions

- E 01. Eastern Cooperative Oncology Group (ECOG) performance status of  $\geq 2$ .
- E 02. Predicted life expectancy  $\leq 3$  months.
- E 03. Active brain metastases or leptomeningeal metastases.
- Patients with previously treated brain metastases are eligible provided they are clinically stable for at least 4 weeks with no evidence of new or enlarging brain metastases and have not received corticosteroids at least 2 weeks prior to first IMP administration (Note: participants with brain involvement due to direct extension of invading tumor, rather than metastasis, may be allowed to enroll if they do not require greater than 10 mg prednisone daily, after discussion and approval from the Sponsor).
  - Patients with asymptomatic brain metastases (ie, no neurological symptoms, no requirements for corticosteroids, and no lesion  $>1.5$  cm) are eligible but will require regular imaging of the brain as a site of disease.
- E 04. History of allogenic tissue/solid organ transplant.
- E 05. Treatment-related immune-mediated (or immune-related) AEs from immune-modulatory agents (including but not limited to anti-PD-1/PD-L1 agents and anti-cytotoxic T lymphocyte associated protein 4 monoclonal antibodies) that caused permanent discontinuation of the agent, or that were Grade 4 in severity.
- E 06. Last administration of prior antitumor therapy (chemotherapy, targeted agents, and immunotherapy) or any investigational treatment within 28 days or less than 5 times the half-life, whichever is shorter; major surgery or local intervention within 28 days prior to first IMP administration.
- E 07. Comorbidity requiring corticosteroid therapy ( $>10$  mg prednisone/day or equivalent) within 2 weeks of IMP initiation. Inhaled or topical steroids are permitted, provided that they are not for treatment of an autoimmune disorder. Participants who require a brief course of steroids (eg, as prophylaxis for imaging studies due to hypersensitivity to contrast agents) are not excluded.
- E 08. Antibiotic use (excluding topical antibiotics)  $\leq 14$  days prior to first dose of IMP, or any serious systemic fungal, bacterial, viral (excluding viral infection settings as described in E 15), or other infection that is not controlled.

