- E 09. Severe or unstable cardiac condition within 6 months prior to starting study treatment, such as congestive heart failure (New York Heart Association Class III or IV), cardiac bypass surgery or coronary artery stent placement, angioplasty, left ventricular ejection fraction (LVEF) below 50%, unstable angina, medically uncontrolled hypertension

(eg,  $\geq 160$  mmHg systolic or  $\geq 100$  mmHg diastolic), uncontrolled cardiac arrhythmia requiring medication ( $\geq$  Grade 2, according to NCI-CTCAE v5.0), or myocardial infarction.

- E 10. Ongoing AEs caused by any prior anticancer therapy  $\geq$  Grade 2 (NCI-CTCAE Version 5.0). Participants with Grade 2 peripheral neuropathy, or Grade 2 alopecia, are permitted. Participants with endocrine-related AEs Grade  $\leq 2$  requiring treatment or hormone replacement may be eligible.

Note: If the participant had major surgery, the participant must have recovered adequately from the procedure and/or any complications from the surgery prior to starting study intervention.

- E 11. Active, known, or suspected autoimmune disease that has required systemic treatment in the past 2 years (ie, with use of disease modifying agents, corticosteroids or immunosuppressive drugs), except controlled by replacement therapy (eg, thyroxine, insulin, or physiologic corticosteroid replacement therapy for adrenal or pituitary insufficiency, etc). The following are not exclusionary: vitiligo, childhood asthma that has resolved, psoriasis that does not require systemic treatment.
- E 12. History of (non-infectious) pneumonitis / interstitial lung disease that required steroids or has current (non-infectious) pneumonitis / interstitial lung disease.
- E 13. Participant who has received prior radiotherapy within 2 weeks of start of study intervention. Participants must have recovered from all radiation-related toxicities, not require corticosteroids, and not have had radiation pneumonitis. A 1-week washout is permitted for palliative radiation ( $\leq 2$  weeks of radiotherapy) to non-CNS disease.
- E 14. Receipt of a live or live-attenuated virus vaccine within 28 days of planned treatment start. Seasonal flu vaccines that do not contain live virus are permitted.

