### **6.8.1 Acceptable concomitant medications**

All treatments that the Investigator considers necessary for a participant's welfare may be administered at the discretion of the Investigator in keeping with the community standards of medical care. All concomitant medication will be recorded on the e-CRF including all prescription, OTC, herbal supplements, and IV medications and fluids. If changes occur during the trial period, documentation of route, and date will also be included on the e-CRF.

Palliative and supportive care is permitted during the course of the trial for underlying medical conditions and management of symptoms. Surgery or radiotherapy for tumor control is not permitted during the study; however, radiotherapy or procedures for symptom management is allowed after discussion with and approval by the Sponsor.

All concomitant medications received within 28 days before the first dose of trial treatment through the Follow-up Visit should be recorded.

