## 8 STUDY ASSESSMENTS AND PROCEDURES

- Study procedures are summarized in this section and their timing is presented in the SoA. Protocol waivers or exemptions are not allowed.
- Adherence to the study design requirements, including those specified in the SoA, is essential and required for study conduct.
- All screening evaluations must be completed and reviewed to confirm that potential participants meet all eligibility criteria. The Investigator will maintain a screening log to record details of all participants screened and to confirm eligibility or record reasons for screening failure, as applicable.
- Procedures conducted as part of the participant's routine clinical management (eg, blood count) and obtained before signing of the ICF may be utilized for screening or baseline purposes provided the procedures met the protocol-specified criteria and were performed within the time frame defined in the SoA.
- During the screening period, demography, medical/surgical, and disease history will be evaluated. Demography includes age, gender, race, and ethnicity. Medical/surgical history includes relevant history of previous pathologies and smoking status. Disease history includes stage at diagnosis and at study entry, and previous anti-tumor therapy (type, duration, reason for discontinuation and response to the therapy). In addition, results of driver gene mutation (such as *BRAFV600E* for participants with melanoma) are also to be collected.
- A comprehensive medical history will be assessed for any cardiovascular signs or symptoms prior to treatment, along with a baseline ECG, echocardiogram and troponin level.
- Regular blood samples will be collected from each participant throughout the duration of the study. Repeat or unscheduled samples may be taken for safety reasons or for technical issues with the samples. Details on blood sampling, including the estimated volume collected for each analysis are provided in the laboratory manual.
- For a regional or national emergency declared by a governmental agency, contingency measures are included in [Section 10.11](#).

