### **8.1.1 Assessment of objective response using the most appropriate modality according to the nature of the measurable lesion(s)**

For participants with disease that is measured radiologically according to RECIST 1.1 criteria ([Section 10.9](#)) a CT or magnetic resonance imaging (MRI) for tumor assessment will be performed as detailed in [Section 1.3](#). The choice of whether the imaging is by CT (preferred) or MRI is an Investigator decision. Once the choice of CT scan or MRI has been made, the same imaging technique should be used in a participant throughout the trial.

Baseline imaging should include all known target lesions. Baseline scans must evaluate extent of disease, including imaging of head, chest, abdomen (pelvis is optional) and any other locations with suspicion or evidence of disease involvement. This may be accomplished with CT chest, abdomen, and pelvis with contrast, or CT chest with contrast and MRI abdomen/pelvis with gadolinium.

The initial CT/MRI tumor imaging will be performed within 28 days prior to C1D1. Scans performed as part of routine clinical management are acceptable for use as the screening scan if they are of diagnostic quality and performed within 28 days prior to the date of enrollment. On-study imaging will be performed every 9 weeks ( $63 \pm 7$  days) after the date of first IMP and if clinically indicated. Imaging studies should follow calendar days and should not be adjusted for delays in cycle starts or extension. After Week 45 tumor imaging should be performed every 12 weeks ( $84 \pm 7$  days). Per the primary tumor assessment criteria, after the first documentation of response or the first documentation of progression (if the participant is clinically stable), confirmatory imaging may be performed no fewer than 28 days later. Alternately, the scan performed at the next scheduled time point (eg, every  $63 \pm 7$  days) may be used as confirmation. Tumor assessment is not needed for participants who start another anticancer therapy.

At a minimum, all radiologically measurable target lesions (RECIST 1.1) should be imaged at each response assessment. The same radiologic imaging modality should be used at each response assessment.

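### No rule places the baseline scan after the last radiotherapy to a target lesion, so radiation shrinkage could count towards a confirmed response

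*Protocol*

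**What the plan says.** All references are to the master protocol unless noted.

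- **Target lesions (5.1, I 03).** One measurable lesion is enough for entry. For irradiated fields: "Target lesion(s) may be located in a previously irradiated field if there is documented radiographic disease progression of such lesion(s".
- **Age of the baseline scan (8.1.1; SoA footnote h).** "The initial CT/MRI tumor imaging will be performed within 28 days prior to C1D1". Routine scans qualify: "Scans performed as part of routine clinical management are acceptable for use as the screening scan if they are of diagnostic quality". Section 8 also accepts routine procedures "obtained before signing of the ICF may be utilized for screening or baseline purposes".
- **Radiotherapy before dosing (5.2, E 13).** The general washout is 2 weeks. For short palliative courses to non-CNS disease, "A 1-week washout is permitted for palliative radiation".
- **Other washout (5.2, E 06).** This excludes "major surgery or local intervention within 28 days prior to first IMP administration". Radiotherapy is not named.
- **Radiotherapy during Screening and treatment (6.8.1, 6.8.2).** Radiotherapy for tumor control is prohibited, but "radiotherapy or procedures for symptom management is allowed after discussion with and approval by the Sponsor". Target lesions are not carved out.
- **Re-baselining.** SoA footnote g prefers a new baseline scan after biopsy of a target lesion. Footnote i and section 8.1.1 require imaging after local treatment of brain metastases to show stability. No similar sentence covers an irradiated extracranial target lesion.
- **Response (10.9, 9.4.2).** PR is a fall of at least 30% from the baseline sum of diameters, confirmed at least 4 weeks later. The primary endpoint is ORR per Investigator.

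**The concern.** PR is measured against the baseline sum. If a target lesion is irradiated after that sum is recorded and before the first dose, any shrinkage from the radiotherapy is credited to the study regimen. A participant may have only one target lesion, and then that lesion alone decides the target-lesion response.

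The error would run one way, upward. Section 4.2 reads ORR against historical data without a control arm, so nothing inside the study would offset it. The same responders also enter TTR and CBR. The events that end the BOR window in 9.4.2 (progression, death, cut-off, post-treatment therapy) cannot catch radiotherapy that precedes the first dose.

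**Working it through.** **1. The plan's own figures.** Table 5 gives exact 90% intervals at N = 40. With the Clopper-Pearson formula (lower = 5% quantile of Beta(x, 40 − x + 1); upper = 95% quantile of Beta(x + 1, 40 − x)) all 11 rows reproduce to one decimal. The rows used here are:

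| Responders | ORR | 90% CI |
|---|---|---|
| 8/40 | 20.0% | 10.4 to 33.2 |
| 9/40 | 22.5% | 12.3 to 36.0 |
| 10/40 | 25.0% | 14.2 to 38.7 |

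**2. The time gap.** Gap = oldest permitted baseline scan minus shortest radiotherapy washout.

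- General radiotherapy: 28 − 14 = up to 14 days.
- Palliative non-CNS radiotherapy: 28 − 7 = up to 21 days.

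The routine-scan sentence counts its 28 days back from enrollment rather than from C1D1. I use the stricter limit, which agrees with the 4-week maximum before treatment in section 10.9.

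**3. Which radiotherapy can fall in the gap.** Section 6.8.2 removes tumor-control radiotherapy during Screening. What remains is:

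- radiotherapy for symptoms, approved by the Sponsor under 6.8.1;
- radiotherapy given before consent, after a routine scan that is later adopted as baseline.

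**4. Does I 03 stop it?** The criterion asks for documented progression of the lesion but gives no order relative to the irradiation. Progression seen on the scan that prompted the radiotherapy meets its literal wording.

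**5. Size.** Each false responder adds 1/40 = 2.5 points. The documents give no rate of radiotherapy in this window and no rate of radiation response, so the following is purely illustrative. Let p be the true ORR, f the share of participants whose target disease is irradiated in the gap, and q the chance that a participant who would not otherwise respond reaches PR because of it.

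Observed ORR = p + f(1 − p)q; extra responders = 40f(1 − p)q.

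Assume f from 2.5% to 10% and q from 30% to 70%.

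- p = 19% (pembrolizumab monotherapy, CPS ≥1, substudy 01 section 2.2.3.1). Low end: 0.19 + 0.025 × 0.81 × 0.3 = 19.6%. High end: 0.19 + 0.10 × 0.81 × 0.7 = 24.7%. Extra responders: 0.2 to 2.3 per 40.
- p = 15% (top of the second-line range in section 2.1). Low end: 0.15 + 0.025 × 0.85 × 0.3 = 15.6%. High end: 0.15 + 0.10 × 0.85 × 0.7 = 21.0%. Extra responders: 0.3 to 2.4 per 40.

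For scale, the 90% lower bound is 18.3% at 12/40 and 20.4% at 13/40, so a single responder decides whether it clears 19%.

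**The case against.** Several points on the other side have weight.

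- **A reader might infer that any palliative course between a Day −28 scan and Day 1 satisfies every rule.** It does not. A course given during Screening needs a symptom indication and Sponsor approval. E 36 also lets the Investigator exclude a participant whose therapy might confound the results, and section 10.9 asks for baseline evaluations as near to treatment start as can be managed. These rules narrow the gap. E 36 is discretionary, however, and section 10.9 sets no firm limit other than 4 weeks.
- **The ordinary reading of I 03 is progression after irradiation.** I agree that this is probably the intent; otherwise the condition would do little. The text still does not say it.
- **A reader might infer that E 06 and E 13 contradict each other.** That holds only if the local-intervention clause of E 06 covers radiotherapy. If it does, the 28-day rule closes the gap but conflicts with the shorter washouts in E 13. If it does not, the two are compatible and the gap stays. Both faults cannot hold at once.
- **A false PR is not automatic.** It needs a 30% fall in the sum over up to five target lesions, no new lesion, no non-target progression and a confirming scan. This limits the number affected.
- **The consequences are limited and partly recoverable.** The intervals are descriptive and no hypothesis is tested. Lesion measurements are collected and images retained, so some cases could be traced, and a SAP could declare such lesions not evaluable. It could not recreate a post-radiotherapy baseline scan that was never taken, which is why the point belongs in the protocol.

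**Conclusion.** The point holds as a gap in the definition of baseline and target lesions, not as an error in any stated figure. The rules leave up to 14 or 21 days in which a lesion already measured at baseline can be irradiated, through the two routes above, and the response definition would credit the shrinkage to the regimen.

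The direction for ORR is upward, and likewise for CBR, which counts the same responses. A reader might infer that DoR is inflated too. The documents do not support that, since local shrinkage followed by early progression elsewhere would shorten it.

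The number affected is unknown and probably small. Only the 2.5 points per false responder is firm; the 0.2 to 2.4 extra responders per 40 rest wholly on assumed rates. This is a cheap improvement, not a threat to the study's validity.

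**What to change.** 1. In I 03, state that the documented radiographic progression must post-date the radiotherapy to that lesion.
2. In section 8.1.1 and SoA footnote h (repeated in substudy 01), state that a lesion irradiated after the baseline scan is not used as a target lesion unless the baseline scan is repeated after the radiotherapy.
3. Clarify whether the local-intervention clause of E 06 includes radiotherapy. If it does, E 06 and E 13 must be reconciled. Which washout should apply is a clinical decision for the sponsor.

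The cost is protocol wording plus an occasional repeat scan or the choice of a different target lesion. The first two changes are measurement rules and leave treatment as it is.

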#### Weight (not applicable)

- I 05. Sex

All (male and female)

Contraceptive use by men and women should be consistent with local regulations regarding the methods of contraception for those participating in clinical studies.

- a) Male participants

Male participants are eligible to participate if they agree to the following during the intervention period and for at least 3 days [corresponding to time needed to eliminate SAR444245] after the last dose of SAR444245:

- Refrain from donating or cryopreserving sperm.

PLUS either:

- Be abstinent from heterosexual intercourse as their preferred and usual lifestyle (abstinent on a long term and persistent basis) and agree to remain abstinent.

OR

- Must agree to use contraception/barrier as detailed below
- A male condom with female partner use of an additional highly effective contraceptive method with a failure rate of <1% per year as described in Appendix 4 (Section 10.4) of the protocol when having sexual intercourse with a woman of childbearing potential (WOCBP) who is not currently pregnant, or during homosexual intercourse

b) Female participants

- A female participant is eligible to participate if she is not pregnant or breastfeeding, and at least one of the following conditions applies:
  - Is not a woman of childbearing potential (WOCBP)

OR

- Is a WOCBP and agrees to use a contraceptive method that is highly effective (with a failure rate of <1% per year), with low user dependency, as described in Appendix 4 (Section 10.4) during the intervention period (to be effective before starting the intervention) and for at least 120 days (for Cohorts A1, A2 and B1) or 60 days (for Cohort B2) [corresponding to the time needed to eliminate any study intervention(s)] after the last dose of study intervention and agrees not to donate or cryopreserve eggs (ova, oocytes) for the purpose of reproduction during this period.
- A WOCBP must have a negative highly sensitive pregnancy test (as required by local regulations) within 7 days before the first dose of study intervention.
- Additional requirements for pregnancy testing during and after study intervention are located in Appendix 4 (Section 10.4).
- The Investigator is responsible for review of medical history, menstrual history, and recent sexual activity to decrease the risk for inclusion of a woman with an early undetected pregnancy.

## Informed Consent

- I 06. Capable of giving signed informed consent as described in Appendix 1 of the protocol which includes compliance with the requirements and restrictions listed in the informed consent form (ICF) and in this protocol.

## 5.2 EXCLUSION CRITERIA

Participants are excluded from the study if any of the following criteria apply:

